6.2.6 Visit 5/Week 8 (Day 57 ±5)

The following procedures must be performed and recorded at the Week 8 visit.

1. Obtain pregnancy test and evaluate results, as applicable. If pregnancy test is positive, the subject may continue in the study; however, study drug should be discontinued.
2. Perform lesion mapping and update lesion map with location for any new lesions.
3. Perform scarring/keloid assessment.
4. Weigh returned study drug and review study compliance.
5. Weigh, record, and dispense new supply of study product and dispense subject diary.

6. Review dosing instructions and have subject/caregiver apply daily dose in clinic using the newly dispensed kit.
7. Perform BOTE Inflammation Score (post-dose).
8. Perform Local Skin Reaction Assessment (post-dose).
9. Collect and record AE information for AEs reported.
10. Update concomitant medication information and confirm if any new occurrences of MC were reported in the subject's household.

6.2.7 *Visit 6/Week 12/ET (Day 85 ±5)*

The following procedures must be performed and recorded at the Week 12/ET1 visit.

1. Complete age-matched Dermatology Life Quality Index (DLQI) assessment, as applicable.
2. Obtain pregnancy test and evaluate results, as applicable.
3. Perform lesion mapping and update lesion map with location for any new lesions.
4. Perform scarring/keloid assessment
5. Perform a brief physical examination.
6. Subject/caregiver administer final dose of study drug from previously dispensed kit.
7. Perform BOTE Inflammation Score (post-dose).
8. Perform Local Skin Reaction Assessment (post-dose).
9. Weigh returned study drug and review study compliance.
10. Collect and record AE information for AEs reported.
11. Update concomitant medication information and confirm if any new occurrences of MC were reported in the subject's household.

6.2.8 *Visit 7/Week 16 and Visit 8/Week 20 (Day 113 +/- 7 days; Day 141 +/- 7 days)*

The following procedures must be performed and recorded at the Week 16 and Week 20 visits. It is expected that these visits should be done by telephone.

1. Collect and record information for new and ongoing AEs, including recurrence of MC.
2. Update concomitant medication information.

6.2.9 *Visit 9/Week 24 (Day 169 +/- 7 days)*

The following procedures must be performed and recorded at the Week 24 visit.

1. Perform scarring/keloid assessment.
2. Collect and record information for new and ongoing AEs, including subject recurrence of MC.

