4. STUDY DESIGN AND PLAN

This is a Phase 3 multi-center, randomized, double-blind, vehicle-controlled, parallel group study to be conducted in approximately 340 subjects ≥ 6 months of age with MC. After obtaining informed consent/assent, subjects who satisfy entry criteria will be randomized to a 2:1 (active:vehicle) scheme. Subjects receiving current treatment for MC at the time of the Screening Visit will enter a washout period of up to 14 days prior to randomization. In the event no washout period is required, Screening and Baseline visit activities may be combined into a single visit. At randomization, subjects will be stratified into 4 strata corresponding to the cross-classification of household number of randomly assigned subjects (1 subject per household vs 2 subjects per household) and investigator type (dermatologist vs other). Households randomizing 2 subjects will receive the same treatment assignment for both subjects. Up to 2 subjects from the same household may be randomly assigned on the same day, if both individually meet all inclusion and exclusion criteria. For subjects in the same household, Screening can occur on different days; however, the baseline visit must occur on the same day.

Subjects or their caregivers will apply SB206 12% or Vehicle Gel QD for a minimum of 4 weeks and up to 12 weeks to all lesions identified at Baseline and new treatable lesions that arise during the course of the study. Subjects or their caregivers will continue to treat the area until the next scheduled visit even if the lesion(s) clear. If the investigator determines all lesions are cleared at a clinic visit, the treatment may stop. At Weeks 2, 4, 8 and 12, the investigator will count and record the number of active (raised, treatable) molluscum lesions per body area. At Weeks 2, 4,

and 8, the investigator will determine if new lesions have occurred since the last visit, and the subject or caregiver will be instructed by the investigator to re-initiate treatment. If treatment is stopped due to clearance, subjects will continue regularly scheduled visits through Week 24.

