7. NOTATION OF TREATMENT GROUPS AND VISITS

Analysis visits

Baseline is defined as the last nonmissing value recorded prior to the first application of study drug. If time is not recorded and the assessment was on the same day as the first application of study drug, then it will be assumed the assessment occurred prior to the application of study drug. The baseline record will have an analysis visit of “Baseline”.

For all evaluations of all parameters, assessments will be analyzed according to the visit at which they occurred (i.e., per the eCRF visit label). In order to account for the fact that the Week 12 and Early Termination visits are collected on the same eCRF in the database, a check against the Study Exit form will be made to determine if the visit is a Week 12 or an Early Termination Visit. If the visit is an Early Termination visit, then the visit will be mapped according to the table below. If there is no corresponding Study Exit form on the same date, then it will be considered a Week 12 visit. If there is no assessment in a given visit, then the following visit windows will be applied to determine if an unscheduled visit may be used:

Visit	Analysis Visit	Target Study Day	Study Day Analysis Window
Week 2 (± 3 days)	Week 2	15	Day 12 to 22
Week 4 (± 5 days)	Week 4	29	Day 23 to 43
Week 8 (± 5 days)	Week 8	57	Day 44 to 71
Week 12 (± 5 days)	Week 12	85	Day 72 to 98

Days are measured from the date of randomization. Study days corresponding to measurements are calculated as:

- Assessment date – date of randomization + 1, if assessment date is on or after the date of randomization.
- Assessment date – date of randomization, if measurement date is before the date of randomization.

In the event of multiple unscheduled records falling in the same analysis window, the assessment which is closest to the target study day will be chosen for analysis.

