10.1 Efficacy Endpoints

The primary efficacy endpoint is the proportion of subjects with complete clearance of all treatable MC at Week 12.

The secondary efficacy endpoint is the proportion of subjects with complete clearance of all treatable MC at Week 8.

Complete clearance is defined as having a total number of lesions count of 0.

The exploratory endpoints are the following:

- Proportion of subjects with complete clearance of all treatable MC at Week 2 and Week 4 visits
- Proportion of subjects achieving at least a 95% reduction from Baseline in the number of all treatable MC at each visit (Weeks 2, 4, 8, 12)
- Proportion of subjects achieving at least a 90% reduction from Baseline in the number of all treatable MC at each visit (Weeks 2, 4, 8, 12)
- Proportion of subjects achieving at least a 75% reduction from Baseline in the number of all treatable MC at each visit (Weeks 2, 4, 8, 12)
- Percent change from Baseline in number of treatable MC at each visit (Weeks 2, 4, 8, 12)
- Change from Baseline in number of treatable MC at each visit (Weeks 2, 4, 8, 12)
- Proportion of subjects who have a recurrence of MC after the first visit at which complete clearance was observed, defined as the total lesion count being greater than 0 at any point after achieving a count of 0

- Time to complete clearance of all treatable MC, defined as the days between the date of first dose and the first date of clearance. Subjects who do not achieve complete clearance will be censored at the date of the last lesion count assessment.
- Proportion of subjects with scarring, defined as an answer of Yes to either question on the Scarring/Keloid Assessment eCRF page: “Was the presence of a scar > 1 mm deep and/or 5 mm wide noted?” or “Was the presence of a scar noted?”, after clearance of lesion(s) at each visit (Weeks 4, 8, 12, 24)
- Proportion of subjects with keloid or hypertrophic scar, defined as an answer of Yes to the Scarring/Keloid Assessment eCRF page question “Was the presence of a keloid or hypertrophic scar noted?”, after clearance of lesion(s) at each visit (Weeks 4, 8, 12, 24)
- Change from Baseline of the composite score from age-matched (at Baseline) Dermatology Life Quality Index (DLQI) or Children’s Dermatology Life Quality Index (CLDQI) assessment at Week 12
- Subject-reported spread to household members as measured by any new occurrence of MC in household members of subjects at each visit (Weeks 2, 4, 8, 12, 16, 20, 24)

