11.3 Exploratory Analyses

The exploratory endpoints based on the proportion of subjects achieving complete clearance or 75%, 90%, or 95% reductions will be analyzed in the same manner as the primary endpoint.

Since the within-household correlation is expected to be small and the change and percent change from Baseline in the number of treatable MC are exploratory, they will be analyzed using a repeated measures mixed model for the respective visits with the same covariates as the primary model together with visits and treatment by visit; an unstructured covariance matrix will be utilized. If the calculation of the percent change from baseline is influenced by outliers with calculated values >100%, then the influence of outliers will be avoided for analysis by censoring them so that all values were in the range of -100% to 100%. If the model fails to converge, then other correlation structures will be explored.

Since the within-household correlation is expected to be small and time to first complete clearance of all MC is exploratory, it will be analyzed using Kaplan-Meier methods. The number and percentage of subjects achieving complete clearance, number and percentage of censored subjects, and Kaplan-Meier estimates of first quartile, median, and third quartile will be summarized by treatment group. Differences in Kaplan-Meier curves between the treatments will be tested for significance using a stratified log-rank test.

The proportion of subjects with scarring and the proportion of subjects with keloid or hypertrophic scarring will be summarized descriptively at each visit.

The change from Baseline of the composite score from age-matched (at Baseline) DLQI/CDLQI will be summarized descriptively and separately for each questionnaire. The scoring algorithms are detailed in [Appendix A](#). The CDLQI will be examined in the following Week 12 response categories: complete clearance, 95% reduction in lesion counts, 90% reduction in lesion counts, and subjects who did not achieve complete clearance. Additionally, the changes from Baseline in the following subscales: Symptoms and Feelings, Daily Activities, Leisure, Work and School, Personal Relationships, and Treatment, for DLQI, and Symptoms and Feelings, Leisure, School or Holidays, Personal Relationships, Sleep, and Treatment, for CDLQI, and each question will be summarized descriptively.

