14.2.3.2.1	Summary of a 95% Reduction in Lesion Counts from Baseline Response by Visit	ITT
14.2.3.2.2	Summary of a 90% Reduction in Lesion Counts from Baseline Response by Visit	ITT
14.2.3.2.3	Summary of a 75% Reduction in Lesion Counts from Baseline Response by Visit	ITT
14.2.3.3.1	Percent Change from Baseline in Lesion Count by Visit	ITT
14.2.3.4.1	Change from Baseline in Lesion Count by Visit	ITT
14.2.3.5	Summary of Recurrence after Complete Clearance	ITT
14.2.3.6.1	Kaplan-Meier Estimates of Time to Complete Clearance (Days) from Start of Dosing	ITT
14.2.3.7	Summary of Scarring and Keloid by Visit	ITT
14.2.3.8.1	Summary of the Dermatology Life Quality Index (DLQI) and Subscales by Visit	ITT
14.2.3.8.2	Summary of the Dermatology Life Quality Index (DLQI) Individual Questions by Visit	ITT
14.2.3.8.3.1	Summary of the Children's Dermatology Life Quality Index (CDLQI) and Subscales by Visit	ITT
14.2.3.8.3.2	Summary of the Children's Dermatology Life Quality Index (CDLQI) and Subscales by Visit	ITT: Complete Responders at Week 12
14.2.3.8.3.3	Summary of the Children's Dermatology Life Quality Index (CDLQI) and Subscales by Visit	ITT: Subjects with at least a 95% Reduction in

Table Number	Table Title	Analysis Population
		Lesion Counts at Week 12
14.2.3.8.3.4	Summary of the Children's Dermatology Life Quality Index (CDLQI) and Subscales by Visit	ITT: Subjects with at least a 90% Reduction in Lesion Counts at Week 12
14.2.3.8.3.5	Summary of the Children's Dermatology Life Quality Index (CDLQI) and Subscales by Visit	ITT: Subjects who did not Achieve Complete Clearance at Week 12
14.2.3.8.4	Summary of the Children's Dermatology Life Quality Index (CDLQI) Individual Questions by Visit	ITT
14.2.3.9	Summary of Increase in Subject-Reported Spread to Household Members by Visit	ITT
14.2.3.10.1	Summary of Lesion Counts by Highest Dichotomized BOTE Score	ITT
14.2.3.10.3	Percent Change from Baseline in Lesion Count over Time by Dichotomized Week 2 BOTE Score	ITT
14.2.3.10.4	Summary of Complete Clearance by Visit and Dichotomized Week 2 BOTE Score	ITT
14.2.3.10.5	Summary of the Beginning of the End (BOTE) Inflammation Score Results by Visit	Safety
14.3	Safety data	
14.3.1	Displays of Adverse Events	
14.3.1.1	Overall Summary of Treatment-Emergent Adverse Events	Safety
14.3.1.2	Summary of Treatment-Emergent Adverse Events by System Organ Class and Preferred Term	Safety

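### Dating clearance and final censoring by actual visit day inflates the last days of the time-to-clearance Kaplan-Meier curve, so a median may be reported although fewer than half of subjects cleared

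*Combined protocol and SAP*

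**What the plan says.** The final SAP, section 10.1, defines the endpoint as "Time to complete clearance of all treatable MC, defined as the days between the date of first dose and the first date of clearance". Its censoring rule is "Subjects who do not achieve complete clearance will be censored at the date of the last lesion count assessment".

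Section 4 of the SAP fixes when clearance can be observed: "At Weeks 2, 4, 8 and 12, the investigator will count and record the number of active (raised, treatable) molluscum lesions per body area". The protocol's Week 12 visit (section 6.2.7) is headed "Visit 6/Week 12/ET (Day 85 ±5", that is, Days 80 to 90. The follow-up part of protocol Table 1 schedules no lesion count, so a completer's last count is normally his own Week 12 visit.

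Section 11.3 applies ordinary Kaplan-Meier methods. "Kaplan-Meier estimates of first quartile, median, and third quartile will be summarized by treatment group", together with the numbers and percentages cleared and censored, and the arms are "tested for significance using a stratified log-rank test". Appendix D titles Table 14.2.3.6.1 "Kaplan-Meier Estimates of Time to Complete Clearance (Days) from Start of Dosing" and lists the matching plot as Figure 14.2.3.6.2.

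Section 7 says that "assessments will be analyzed according to the visit at which they occurred (i.e., per the eCRF visit label"). That rule decides which visit a record belongs to. It does not replace the actual date in a time variable measured in days. Sections 10.1 and 11.3 and Appendix B contain no rule for nominal visit days, grouped or interval-censored estimation, or truncation of the curve.

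**The concern.** In the Week 12 window each subject is examined once, and that examination decides whether he is an event or a censoring. A subject found with lesions on Day 80 is removed from the risk set, and Kaplan-Meier then treats him as someone who might still clear at the rate seen on Days 81 to 90. One visit's clearance probability is therefore applied again and again to a shrinking risk set. On the last day of the window the risk set is only those seen that day. This needs no dropout.

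At stake is what the report shows for this endpoint. A median near the end of the window could be printed, and the plotted curve could pass 50%, in an arm where about a third of subjects cleared. A median time to clearance is easily quoted and is read as meaning that half cleared.

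**Working it through.** **Inputs from the documents.** SAP section 5: 227 SB206 and 113 vehicle subjects; vehicle rate 18%; difference 18 points, hence 36% on SB206. Protocol: Week 12 at Day 85 ±5.

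**Assumed, because the documents do not give them.** The share cleared by Week 8 (F8), the spread of visit days, and dropout.

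**The plan's own figure.** Pooled two-proportion test, two-sided 0.05: pooled rate = (227×0.36 + 113×0.18)/340 = 0.300; SE under H0 = √[0.300×0.700×(1/227 + 1/113)] = 0.0528; SE under H1 = √(0.36×0.64/227 + 0.18×0.82/113) = 0.0482; power = Φ[(0.18 − 1.96×0.0528)/0.0482] = 94.4%. The other two cases give 93.4% and 82.8%. The SAP states 94%, 93% and 83%, so the inputs are reproduced.

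**Closed form for the curve.** Let h = (F12 − F8)/(1 − F8) be the chance of clearing at Week 12 among those not yet clear. With visits spread evenly over 11 days and no dropout, the Kaplan-Meier factor for the whole window is ∏(1 − h/k), k = 1 to 11. On a single common day it would be 1 − h.

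SB206, F8 = 20%, F12 = 36%: h = 0.16/0.80 = 0.20. The product is 0.528 instead of 0.80, so the curve ends at 1 − 0.80×0.528 = 58% instead of 36%. Vehicle, F8 = 9%, F12 = 18%: h = 0.09/0.91 = 0.099. The product is 0.736, so the curve ends at 1 − 0.91×0.736 = 33% instead of 18%.

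Day by day, with the number at risk equal to 227×0.80×(days left)/11:

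| Day | SB206 at risk | SB206 curve | Vehicle curve |
|---|---|---|---|
| 80 | 182 | 21% | 10% |
| 85 | 99 | 31% | 15% |
| 87 | 66 | 37% | 19% |
| 88 | 50 | 41% | 22% |
| 89 | 33 | 47% | 26% |
| 90 | 17 | 58% | 33% |

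At Day 85 both curves are below the true rates, because half the window is still to come. The SB206 curve passes 36% only on Day 87. About half of the 22-point excess at the end arises on Day 90, with about 17 subjects at risk. SB206 crosses 50% on Day 90, so a median is reported. Vehicle crosses 25% on Day 89, so a first quartile is reported although only 18% cleared.

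**Simulation over other assumptions.** SB206, true 36%, no dropout; value at the end of the curve:

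| Visit days in 80-90 | F8 = 28% | F8 = 22% | F8 = 14% |
|---|---|---|---|
| Uniform | 49% | 56% | 63% |
| Triangular | 54% | 62% | 70% |
| Normal, SD 2 days | 54% | 63% | 72% |
| 60% exactly on Day 85 | 51% | 58% | 65% |
| Runs reporting a median | 40-56% | 79-86% | 94-99% |

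With about 32% cleared by Week 8 the curve ends at about 42-46%. A 10% dropout moves the results by about 1 point or less. If 5% of Week 12 visits fall late, on Days 91-98, the end rises to 57-78%. The vehicle curve, true 18%, ends at about 30-42%, with a median in 3-24% of runs. With 90% of visits on Day 85 the SB206 curve still ends at 52-60% (F8 of 27% and 20%), because its end then rests on about two subjects.

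**Log-rank test.** An unstratified version, run with 22% and 11% cleared by Week 8, gave type I error of 4.1-4.3% and power of about 92% for 36% against 18%. The stratified test was not simulated.

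**After the fix.** With Week 12 events and censorings on one common day the estimate is 36% and 18%, and no simulated run reports a median.

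**The case against.** A reader might infer that the method overstates clearance at Week 12 and exaggerates the difference between arms. The documents do not support that. The SAP's target day for Week 12 is Day 85, where the closed form gives 31.1% against 15.4%, a difference of 15.7 points and so below the planned 18. Section 11.3 plans no Kaplan-Meier rate at a fixed day and no Kaplan-Meier difference between arms. It also places the crude percentage cleared beside the quartiles, so a reader of Table 14.2.3.6.1 could see that a reported median conflicts with it. This objection stands, and it confines the point to the quartiles and the plotted tail.

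The comparison with the primary table is not like for like either. That table counts subjects clear at Week 12. This endpoint counts first clearance at any visit, and recurrence is a separate endpoint, so some gap is legitimate. It does not account for the inflation, which arises with recurrence set to zero.

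A reader might also blame the censoring rule alone. Anyone censored at a last assessment without the event is event-free at that time, and the same rule gives no bias when all visits fall on one day. The fault lies in combining one-look, visit-driven event times with scattered final visit dates.

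Finally, the size depends on inputs that the documents do not give. That is fair, and it is why a range is stated.

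**Conclusion.** The rule as written can report a median that was not reached, and it draws a misleading end to the Kaplan-Meier curve. At a true 36% the SB206 curve ends at about 50-70% under plausible assumptions, at about 42-46% if nearly all clearers cleared by Week 8, and at 36% if every Week 12 visit falls on the same day. At Day 85 it reads about 29-36%. The direction at the end of the curve follows from the SAP text whenever Week 12 visit days vary and some first clearances occur at Week 12. The size rests on the assumed Week 8 rate and visit-day spread. It also treats 36% as the share ever cleared, which recurrence before Week 12 could make somewhat higher.

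The crude clearance percentage, the log-rank test, and the Week 12 and Week 8 analyses are not materially affected. The endpoint is exploratory and lies outside the fixed-sequence test. The point is minor.

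**What to change.** In SAP 10.1 and 11.3, assign both events and censoring to the scheduled day of the visit at which the count was made (Day 15, 29, 57 or 85), with clearances on a day counted before censorings on that day. Visits labelled Week 12 but held outside the window then take Day 85 as well. Alternatively, use an interval-censored or grouped-time estimator, which should target the same values (this was not run separately).

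Report cumulative clearance at Weeks 2, 4, 8 and 12 by arm, and report a quartile only if the visit-based cumulative clearance reaches it.

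The cost is a change of wording and of the derivation of one time variable, with no new data. Time is then expressed in scheduled visits rather than exact days, a precision that four counts do not provide.

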Clinically significant LSRs that are reported as adverse events and/or subject reported intolerance (i.e. itching, pain) may result in an investigator directed temporary treatment hold (drug holiday), and topical corticosteroids may be used to treat LSRs for up to 2 weeks. The subject may re-initiate study drug treatment prior to the next scheduled visit. Upon re-initiation of study drug treatment, if a subject develops worsening LSRs, allergic contact dermatitis may be suspected. The investigator may take photographs of the suspected allergic contact dermatitis and discuss possible confirmation of allergic contact dermatitis with the CRO medical monitor. The investigator should also discuss necessity of patch testing with the subject/caregiver. The investigator will then discontinue the subject from study drug treatment and treat the area(s) with corticosteroids for up to 2 weeks. If the subject provides consent/assent, the investigator will consult the contract

research organization (CRO) medical monitor to implement the process for patch testing.

Adverse events will be assessed and collected after the initiation of study drug treatment through the end of the subject's last visit. Treatment related adverse events will be followed up until resolution or up to one year after last treatment, whichever is sooner.

Scar formation will be assessed starting at the Week 4 visit through Week 12 and again at Week 24. The investigator will map locations of the molluscum lesions at Baseline. Additional lesions identified through Week 12 will be added to the map. Using the map as a guidance, the investigator will assess the treated areas for scar/keloid formation. The investigator will count and record the number of active (raised, treatable) molluscum lesions per body area. If a scar is larger than 5mm in diameter and/or larger than 1 mm deep, this will be considered an adverse event for the purposes of this study. In addition, keloid/hypertrophic scars will also be recorded as adverse events. Any scars <5mm in diameter and/or <1mm deep will not be considered AEs since these are considered part of the normal healing.

If a subject's treatment is discontinued by the investigator or the subject because of an AE, that AE should be indicated as the reason for treatment discontinuation. All subjects will be encouraged to remain in the study throughout the 24-week study duration.

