Clinically significant LSRs reported as AEs and/or subject reported intolerance (i.e. itching, pain) may result in an investigator-directed temporary treatment hold (drug holiday), and topical corticosteroids may be used to treat LSRs for up to 2 weeks. If a drug holiday is prescribed, Investigational product (IP) will still be dispensed at the clinic visit to ensure the subject may resume dosing prior to the next clinic visit. The subject may reinitiate study drug treatment prior to the next scheduled visit. Upon re-initiation of study drug treatment, if a subject develops worsening LSRs, allergic contact dermatitis may be suspected. The investigator may take photographs of the suspected allergic contact dermatitis and discuss possible confirmation of allergic contact dermatitis with the CRO medical monitor. The investigator should also discuss necessity of patch testing with the subject/caregiver. The investigator will then discontinue the subject from study drug treatment and treat the area(s) with corticosteroids for up to 2 weeks. If the subject provides consent/assent, the investigator will consult the clinical research organization (CRO) medical monitor to implement the process for patch testing.

Adverse events will be assessed and collected after the initiation of study drug treatment through the end of the subject's last visit. Treatment-related adverse events will be followed up until resolution or up to one year after last treatment, whichever occurs earlier.

Scar formation will be assessed starting at the Week 4 visit through Week 12 and again at Week 24. The investigator will map locations of the molluscum lesions at Baseline. Additional lesions identified through Week 12 will be added to the map. Using the map as a guidance, the investigator will assess the treated areas for scar/keloid formation. MC lesions may resolve with pitted scars (indentation), and the small scars that maintain original MC size (<5 mm) and less than 1 mm in depth will heal over time. Any pitted scars <5 mm in diameter and <1 mm in depth will not be considered AEs since these are considered part of the normal healing process. . If a scar is larger than 5 mm in diameter or greater than 1 mm in depth, this will be considered an adverse event for the purposes of this study. In addition, keloid/hypertrophic scars will also be recorded as adverse events.

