7.2.6 Scarring/Keloid Assessment

Scar formation will be assessed starting at the Week 4 visit through Week 12, and again at Week 24. For the purposes of this study, scar is defined as follows: pitted scars with ≥ 5 mm in diameter or ≥ 1 mm in depth, and hypertrophic/keloid scars originated from MC lesion. Pitted scars < 5 mm in diameter and < 1 mm in depth originated from MC lesion are considered part of normal healing process and will not be captured as AEs.

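### SAP 10.1 counts scarring on a Yes to either a question with a size limit or one with none, so the reported proportion may not be the scar that Protocol 7.2.6 defines

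*Combined protocol and SAP*

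**What the plan says.** Protocol 3.3 lists, as an exploratory endpoint, the proportion of subjects who develop scars after lesion clearance at Weeks 4, 8, 12 and 24. That line gives no size limit. The definition is in Protocol 7.2.6, which sets it for the whole study: "scar is defined as follows: pitted scars with ≥ 5 mm in diameter or ≥ 1 mm in depth, and hypertrophic/keloid scars". Pitted scars below both limits "are considered part of normal healing process and will not be captured as AEs".

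SAP 10.1 puts the endpoint into operation as "Proportion of subjects with scarring, defined as an answer of Yes to either question on the Scarring/Keloid Assessment eCRF page". The two questions are:

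- **A, thresholded:** "Was the presence of a scar > 1 mm deep and/or 5 mm wide noted"
- **B, no stated threshold:** "Was the presence of a scar noted"

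Keloid or hypertrophic scarring is a separate endpoint with its own eCRF question. SAP 11.3 summarizes both descriptively by visit. The definition is the same in all three SAP texts supplied.

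The size limit is not worded consistently elsewhere:

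- **Protocol Synopsis:** "Any scars <5mm in diameter and/or <1mm deep will not be considered AEs since these are considered part of the normal healing"
- **Protocol 4.1:** "Any pitted scars <5 mm in diameter and <1 mm in depth will not be considered AEs"
- **Protocol 9.1:** pitted scars at least 1 mm deep are AEs, as are scars bigger than the original lesion or reaching beyond the treated area, and hypertrophic/keloid scars.
- **SAP section 4:** a new scar seen after treatment is an AE, with no size limit.

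SAP section 2 cites protocol version 1.0 and eCRF version 3.0. SAP section 14 lists four changes from the protocol, none of which concerns scars.

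**The concern.** The protocol draws a line between a scar and an expected residue of healing. Its definition of clearance in 7.1.1 allows a small, shallow pit to remain in a lesion counted as clear. The SAP endpoint accepts a Yes to a question that does not state that line. If sites answered that question literally, the table headed as scarring would mix protocol-defined scars with pits the protocol calls normal healing, and a reader could not separate them.

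This matters because resolution without scarring is part of the stated rationale for SB206 (Synopsis and Protocol 1.2). The table could also disagree with AE data collected under a size limit.

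**Working it through.** The plan gives no scar rate, so there is no figure to reproduce. The check is on the logic of the rule, followed by an illustration under stated assumptions.

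**Step 1: which scars are classified differently.** Inputs are the 7.2.6 limits (diameter ≥ 5 mm or depth ≥ 1 mm) and question A read as depth > 1 mm or width > 5 mm. Question B is read literally, so any scar is a Yes.

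| Depth, width | 7.2.6 scar | A | B, literal | SAP endpoint |
|---|---|---|---|---|
| 0.5 mm, 3 mm | No | No | Yes | Counted |
| 0.5 mm, 6 mm | Yes | Yes | Yes | Counted |
| 1.5 mm, 3 mm | Yes | Yes | Yes | Counted |
| 1.5 mm, 6 mm | Yes | Yes | Yes | Counted |
| 1.0 mm, 3 mm | Yes (1 ≥ 1) | No (1 is not > 1) | Yes | Counted |

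The SAP endpoint and 7.2.6 part only in the first row, the pit below both limits. The last row shows a separate mismatch: question A alone misses a scar exactly at a limit.

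**Step 2: what the either-question rule does.** There are three possibilities.

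- Both questions asked at the same visit, B read literally: every A is also a B, so A or B equals B, and the limit drops out.
- B answered under the 7.2.6 definition: a sub-threshold pit gets No, and the endpoint stays at protocol-defined scars. B would then also take in hypertrophic/keloid scars and overlap the separate keloid endpoint.
- A and B come from different eCRF versions: the rule simply maps whichever question was asked, and pools answers with and without the limit.

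**Step 3: possible size.** Let *a* be the proportion of subjects with an above-threshold scar, *s* the proportion with sub-threshold pits only, and *f* the share of the latter who receive a Yes. Then

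reported proportion = *a* + *f* × *s*.

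Assume *a* = 2% to 5% and *s* = 5% to 20%.

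| *f* | Low end | High end |
|---|---|---|
| 0 (B carries 7.2.6) | 2% + 0 = 2% | 5% + 0 = 5% |
| 0.5 (mixed practice) | 2% + 0.5 × 5% = 4.5% | 5% + 0.5 × 20% = 15% |
| 1 (B literal) | 2% + 5% = 7% | 5% + 20% = 25% |

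The values of *a*, *s* and *f* are assumptions and only show how far the definition could move the figure.

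**The case against.** The best defence is that 7.2.6 fixes the meaning of scar throughout the study, so an investigator applying it answers No to question B for a small pit and nothing is miscounted. How B was answered depends on eCRF completion instructions that are not in these documents. This stands as a possibility. Against it, question A would not need to spell out the limit if the word already carried it, and SAP section 4 uses scar with no limit. Neither point settles the matter.

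A reader might infer several stronger things that the documents do not support:

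- **That ordinary healing marks are in fact reported as scarring.** This is a risk that turns on how B was completed. It could concern only small pitted scars; Protocol 7.1.1 lists pigment change separately.
- **That question A is redundant.** This holds only if both questions were answered at the same visit and B was read literally.
- **That SAP section 14 conceals a departure.** The SAP is written to protocol version 1.0, and the documents do not establish that the scar wording in the supplied protocol matches that version. The gap may instead be a SAP that was not updated.
- **That the count is tilted against SB206.** The planning assumption is 36% versus 18% clearance (18% + 18% against 18%), so more SB206 subjects could have residual pits. But the protocol's own endpoint is also scars after clearance, so greater opportunity arises under either definition, and there are no data on direction or size.

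It is also fair to say that the protocol has no single limit to depart from, since the Synopsis, 4.1, 7.2.6 and 9.1 differ. That makes an explicit SAP definition more necessary. Finally, the consequence is limited: the endpoint is not tested, keloid/hypertrophic scarring is reported separately, and individual assessments are listed (Listing 16.2.6.3).

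**Conclusion.** The concern holds as a defect of definition. As written, the SAP rule can count pits that Protocol 7.2.6 excludes, or pool answers given under two definitions, and nothing in the documents tells the reader which has happened. Under the assumed rates the same subjects could be reported as 2–5% or as 7–25% scarred, depending only on how question B was understood. That range rests wholly on assumption. What is established is that the endpoint cannot be interpreted without knowing the meaning of question B. The primary and secondary endpoints, the type I error control and the power are untouched.

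**What to change.** Before the scarring table is produced:

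1. Report questions A and B as separate rows at each visit.
2. Base the protocol-defined scarring row on a Yes to question A or to the keloid/hypertrophic question. Add a footnote that scars exactly at 1 mm or 5 mm cannot be matched to 7.2.6, because the eCRF asks for more than the limit and 7.2.6 includes it. The Yes/No answers already collected cannot recover this.
3. State whether question B was meant to carry the 7.2.6 definition, and show separately any subjects for whom only B was collected.
4. Reconcile the scar wording in the Protocol Synopsis, 4.1, 7.2.6 and 9.1 and in SAP section 4. Which AE criterion should govern is for the sponsor to decide.
5. List any departure that remains in SAP section 14.

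The cost is a SAP definition, one or two extra table rows and a footnote, with no new data.
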